	n=2	n=3	n=4	n=5	n=6	n=7	n=8	n=9	n=10	n=11	n=12
0	E	E	E	E	E	E	E	E	E	E	E
1	S	S	S	S	E	E	E	E	E	E	E
2	U	D	S	S	S	S	S	S	E	E	E
3		U	U	D	D	S	S	S	S	S	S
4			U	U	U	U	D	D	D	S	S
5				U	U	U	U	D	D	D	D
6					U	U	U	U	U	U	U
7						U	U	U	U	U	U

D: De-escalate the dose; E: Escalate the dose; S: Stay at the dose; U: Unacceptable toxicity

Note: If one patient has a DLT event observed in a dose cohort with 1 patient enrolled, additional patients (eg, 1 or 2) may be enrolled for dose escalation assessment.

Dose escalation will stop under any of the following conditions:

- The maximum sample size has been achieved;
- 6-12 patients have been enrolled at a dose that is predicted to be the MTD;
- All doses explored appear to be overly toxic and the MTD cannot be determined.

Intrapatient dose escalation, other than the potential inclusion of priming doses, will not be permitted in this study.

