3.4. MTD Definition

The estimated MTD is the dose level associated with approximately 27.5% of DLT-evaluable patients experiencing a DLT. The target interval for the DLT rate is (22.5%-32.5%). Due to the discreteness of the dose levels and in the interest of the safety of patients, the estimated MTD is the highest tested dose level with DLT rate ≤ 0.325 in at least 6-12 evaluable patients for DLT. The study aims to determine a MTD for a dose regimen that does not include a priming dose administered IV, and an independent MTD for an IV dose regimen that includes a priming dose. In addition, the study aims to determine a MTD for PF-06671008 administered SC and may also determine an independent MTD for a SC dose regimen that includes a priming dose.

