Cohorts of patients could receive doses already tested but a dose that is associated with decision “Dose de-escalate, unacceptable toxicity” cannot be revisited and no more patients should be treated at this dose or higher doses for the remainder of the trial.

The maximum sample size for Part 1 would be N=92 but actual sample size will depend on the underlying dose toxicity profile and variability in actual data realization.

The study will continue accruing until one of the three stopping conditions below is triggered.

The algorithm will stop if any of the following criteria is met:

1. The maximum sample size has been achieved.

2. MTD has been identified with sufficient accuracy: 6 to 12 patients have been accumulated on a dose that is currently estimated to be the MTD; or
3. All doses explored appear to be overly toxic and the MTD cannot be determined.

Due to binomial data variability in small samples, DLTs may be observed in a first cohort(s) by chance even when the true Probability (DLT) is fairly low. This could result in the estimated posterior DLT rate to exceed the targeted 27.5% very early in the trial, triggering an early stop when very few patients (2-4) have been treated. To prevent stopping the trial prematurely in such cases, a step-down option with a lower dose of 1.0 ng/kg is added to the dose grid. This dose will be explored only if a high DLT rate occurs in the first cohort assigned to 1.5 ng/kg, ie, it will not be used as a starting dose and the algorithm will always assign the first cohort of patients to 1.5 ng/kg.

The following table shows the probability of escalating to the next dose level for a range of underlying true DLT rates. For example, for a cohort size of n=3 and for a DLT that occurs in 10% of patients, there is a greater than 90% probability of escalating. Conversely, for a DLT that occurs with a rate of 70%, the probability of escalating is 3%. It is assumed that dose escalation occurs with either 0/3 or 1/6 patients with DLTs.

Probability of Escalating Dose

True underlying DLT rate	10%	20%	30%	40%	50%	60%	70%	80%	90%
Probability of escalating dose	0.91	0.71	0.49	0.31	0.17	0.08	0.03	0.009	0.001

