 - 5 DLTs -> de-escalate (mTPI suggests “remain at the same dose”)
 - 6-11 DLTs -> de-escalate and consider current dose as intolerable
- With 12 patients treated at current dose level
 - 0-2 DLTs -> escalate
 - 3-4 DLTs -> remain at the same dose
 - 5 DLTs -> de-escalate (mTPI suggest “remain at the same dose”)
 - 6-12 DLTs -> de-escalate and consider current dose as intolerable

mTPI Operating Characteristics

This is a dose-escalation study primarily driven by safety. While efficacy endpoints will also be assessed, they will play only a supportive role. The primary safety endpoint will be presence or absence of DLT. The simulation focuses on a follow-up period for DLT assessment and ignores non DLTs toxicities or DLTs occurring outside of this time frame. This simulation refer to the escalation phase after the selection of the priming dose as that will be based on non DLTs lower grade cytokine release (eg < Grade 2; see [Evaluation of a Priming Dose](#)).

This study has been designed to establish the Maximum Tolerated Dose (MTD) defined as the dose that yields approximately 27.5% probability of DLT and considers equivalent doses that yield probability of DLTs in the interval (Equivalence Interval) 22.5% to 32.5%. The 27.5% target was chosen based on safety considerations and is considered appropriate based on simulations and expert input. Since mTPI algorithms are known to assign more patients

above the target dose compared to 3+3 designs, the target was chosen slightly below the maximum acceptable DLT rate of 33.3% (in order to protect study patients from exposure to doses with DLT rate higher than 33%). Doses with an incidence of DLT>33% cannot be selected as MTD in the current protocol therefore the decision rules implemented in the actual study are more conservative of the ones used in this simulation, therefore results of these simulations represent more aggressive scenario. In addition, in the study patients will be enrolled in cohorts of size 2-4 but constant size of 3 was assumed for all simulations.

Table 10. Simulation Parameters Selected for the Final Design

	Final Design Value
Control Parameters	
Cohort size	3 patients
Max doses levels	5 levels
Minimum number of patients on MTD to stop for success	6,9,12 patients
Other parameters	
Max sample size for one regimen of part 1	50 patients
DLT target rate at MTD	pT= 0.275
Equivalence Interval for DLT target rate at MTD	EI: 0.225-0.325
Prior distribution of DLT	Beta(0.5,0.5)

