As expected, those Scenarios in which there are small increases of DLT rate from dose-to-dose present a challenge for the algorithms to find the right dose in terms of sample size, as there will be many “competing” MTD doses. For example in Scenarios #1 and #2 mTPI selects the correct MTD 90% and 44% of the times respectively. Specifically in Scenario #1, mTPI selected the correct MTD 90% of the times compared to 79% by 3+3 but required approximately 5 more patients. Similarly, in Scenario #2, mTPI estimated the correct MTD more often than 3+3 with slight increase in sample size. Also the absolute and relative numbers of toxicity events were comparable. Scenario #5 represents a situation where the DLT curve is very steep and only one dose is within the EI. mTPI selected the correct MTD 66% of the times compared to 31% by 3+3 and required approximately 5 patients more. In all scenarios #1-2-3-4-5 the performance of the mTPI method was always superior to 3+3, selecting the correct MTD at least 13% more often (35% in Scenario #5) and requiring approximately 4 more patients on average.

Stopping rules with 6, 9 and 12 patients on MTD were considered for the mTPI design and compared via simulations. These results are summarized in [Table 13](#). The stopping rule with 9 patients on MTD performed adequately for MTD estimation and required a study sample size comparable to that of 3+3 design ([Table 13](#)). A stopping rule with 12 patients had greater chance of identifying MTD correctly (scenarios 1,2,3,4). However this added benefit came at a price of additional patients. In cases of early toxicity (eg, Scenario 5), where the first tested dose is within the EI, there were no noticeable improvements in quality of correct MTD estimation if 12 patients were required on MTD to stop, rather than 6 or 9.

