In summary, since there was no *a priori* knowledge about the likelihood of a particular toxicity scenario, performance of the mTPI design under all scenarios was taken into consideration in the choice of the final design. Across all scenarios examined, a design employing the mTPI algorithm with at least n=6 at MTD (up to n=12) will have a better chance to estimate MTD correctly compared to a traditional 3+3 design, while the overall proportion of toxicities observed within a study remains acceptable and similar between mTPI and 3+3. mTPI design may result in a longer trial duration compared to the duration of 3+3 design, however, this increase is off-set by a better performance of mTPI in all simulated scenarios. Among many design parameters examined, the stopping rule (number of patients on MTD) had the most impact on the design's performance. As expected, increasing the minimum number of patients treated on MTD prior to stopping leads to a more precise MTD estimation; however this requirement would also lead to larger overall sample size, longer trial duration and greater overall number of toxicities (but not necessarily the proportion of toxicities).

Table 12. Operating Characteristics of the mTPI Design (n at MTF=9) versus Conventional 3+3 Design

DLT Scenario	Design	MTD dose selection decision (proportion)				Av Size	Num Tox	Prop tox
		CORRECT	UNDER	OVER	NA			
1:	3+3	0.79	0.20	-	0.01	17.1	1.0	0.06
	mTPI	0.90	0.10	-	0.00	21.9	1.6	0.07
2:	3+3	0.31	0.66	-	0.03	17.3	2.4	0.14
	mTPI	0.44	0.56	-	0.00	21.1	3.2	0.15
3:	3+3	0.23	0.71	0.03	0.03	17.2	2.9	0.17
	mTPI	0.38	0.45	0.17	0.00	20.9	4.1	0.20
4:	3+3	0.37	0.43	0.09	0.15	12.2	3.1	0.26
	mTPI	0.50	0.26	0.23	0.005	16.2	4.5	0.27
5:	3+3	0.31	-	0.07	0.62	7.7	2.8	0.38
	mTPI	0.66	-	0.18	0.17	11.5	4.3	0.38

[figure not shown]
Table 13. Operating Characteristics of the mTPI Design by Minimum Number of Patients on MTD

mTPI: Dose selection decision (%) by Minimum number of patients on MTD (ie, n=6,9,12)

scenario	N at MTD	% CORRECT	% UNDER	% OVER	% NA	Av Size	Num. Tox	Prop Tox
1	6	0.893	0.108	0.000	0.000	18.837	1.214	0.064
1	9	0.900	0.101	0.000	0.000	21.943	1.564	0.071
1	12	0.956	0.044	0.000	0.000	25.802	2.012	0.078
2	6	0.437	0.563	0.000	0.000	17.600	2.562	0.146
2	9	0.437	0.563	0.000	0.000	21.051	3.233	0.154
2	12	0.544	0.456	0.000	0.000	26.637	4.364	0.164
3	6	0.374	0.434	0.192	0.000	17.277	3.154	0.183
3	9	0.378	0.448	0.174	0.000	20.919	4.109	0.196
3	12	0.460	0.342	0.198	0.000	26.728	5.700	0.213

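### Appendix 7's operating characteristics leave out the 0.325 MTD cap that the study applies; the omission is disclosed but not quantified, and some text and table figures do not agree

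*Protocol*

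**What the plan says.** Protocol Section 3.4 defines the estimated MTD as "the highest tested dose level with DLT rate ≤ 0.325 in at least 6-12 evaluable patients for DLT", and SAP Section 2.2.4 repeats this. Protocol Section 9.2 also excludes doses above 32.5%, with 4 of 10 as its example. Escalation stops once "6 to 12 patients have been accumulated on a dose that is currently estimated to be the MTD" (Section 9.2) or once "6-12 patients have been enrolled at a dose that is predicted to be the MTD" (Section 3.2.2). Section 9.3 allows 1 to 12 patients per dose.

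Appendix 7 reports simulations without the cap, which it writes as 33% beside a maximum acceptable rate of 33.3%. It says the study's rules are more conservative, "therefore results of these simulations represent more aggressive scenario". It then claims for all five scenarios: "In all scenarios #1-2-3-4-5 the performance of the mTPI method was always superior to 3+3, selecting the correct MTD at least 13% more often", with 35% in Scenario 5 and about 4 more patients on average. For Scenario 5 it says: "mTPI selected the correct MTD 66% of the times compared to 31% by 3+3 and required approximately 5 patients more". It reports that a stop at 12 patients finds the MTD more often in Scenarios 1 to 4, and concludes that "increasing the minimum number of patients treated on MTD prior to stopping leads to a more precise MTD estimation".

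**The concern.** The simulated design is not the one the study will run. With the usual patient counts, 2/6, 3/9 and 4/12 are all 0.333 and fail a 0.325 cap. These outcomes are common at a dose whose true rate is near the target, so the cap removes good doses as well as bad ones. The remark about a more aggressive scenario warns only about toxicity. It does not tell the reader that correct selection falls or that more trials end without an MTD. Appendix 7 is the quantitative case for mTPI over 3+3 and for the 6-to-12 stopping size. Its figures are most misleading when toxicity appears at the first dose level. Several figures in its text also disagree with its own Table 12.

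**Working it through.** **Text against Table 12.**
- Gains in correct selection, mTPI minus 3+3, Scenarios 1 to 5: 0.90 − 0.79 = 0.11; 0.44 − 0.31 = 0.13; 0.38 − 0.23 = 0.15; 0.50 − 0.37 = 0.13; 0.66 − 0.31 = 0.35. The minimum is 11 points. The quoted 35% is an absolute difference, so the 13% must be read on that scale too.
- Extra patients in Scenario 5: 11.5 − 7.7 = 3.8.
- Scenario 4, 3+3 row: 0.37 + 0.43 + 0.09 + 0.15 = 1.04. Exact enumeration of 3+3 gives 0.790/0.305/0.233/0.328/0.315 correct. This matches the table except in Scenario 4, where about 0.33 stands against 0.37.

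**Reproducing the stated mTPI figures.** Inputs from Sections 9.2 and Appendix 7: target 0.275, interval 0.225 to 0.325, Beta(0.5, 0.5) prior, exclusion threshold 0.95, five levels, cohorts of 3, maximum 50 patients, and the Table 11 scenarios. Assumption: the MTD is the non-excluded dose whose isotonic estimate is closest to 0.275. Without the cap, at a stop of 9, this gives 0.893/0.430/0.379/0.501/0.659 correct, against 0.900/0.437/0.378/0.504/0.656 in Table 13. Scenario 5 no-MTD is 0.158 against 0.166.

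**Why Scenario 5 is sensitive.** Its only correct dose has a true rate of 0.32. At n = 9 the chance of exceeding the cap is P(X ≥ 3) = 1 − (0.68⁹ + 9·0.32·0.68⁸ + 36·0.32²·0.68⁷) = 1 − (0.031 + 0.132 + 0.248) = 0.59. At n = 6, P(X ≥ 2) = 0.62; at n = 12, P(X ≥ 4) = 0.57.

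**Scenario 5 with a cap, stop of 9.** Gains are against the stated 3+3 value of 0.31.

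| How the cap enters | Correct | Gain (points) | No MTD |
|---|---|---|---|
| Not applied (Table 12) | 0.66 | 35 | 0.17 |
| Governs the stop, at most 12 per dose | 0.43–0.46 | 12–15 | 0.44–0.49 |
| Governs the stop, at most 15 per dose | 0.48 | 17 | 0.43 |
| Governs the stop, no per-dose limit | 0.59–0.61 | 28–30 | 0.30–0.31 |
| Step down at 9 if over the cap | 0.36 | 5 | 0.57 |
| Final selection only | 0.39 | 8 | 0.53–0.54 |
| Exactly 1/3 allowed | 0.54–0.58 | 23–27 | 0.27–0.32 |

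In the no-limit row, 28 points and 0.31 come from pure mTPI decisions; 30 points and 0.30 come from protocol Table 2 decisions.

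**All scenarios, stop of 9, cap at the stop, at most 12 per dose.** Correct is 0.87/0.35/0.35/0.44/0.43, so the gains over stated 3+3 are about 8/4/12/7/12 points. Overestimation in Scenarios 3, 4 and 5 falls from 0.17/0.23/0.18 to 0.08/0.11/0.08. Mean sizes are 22.3/22.9/23.5/18.7/13.7. Subtracting 17.1/17.3/17.2/12.2/7.7 gives 5.2/5.6/6.3/6.5/6.0, a mean of 5.9 extra patients, against 4.0 from Table 12.

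**Selection-only cap.** At a stop of 9 the Scenario 2 gain is about nil. At a stop of 6, correct is 0.77/0.27/0.26/0.34/0.33, or −2/−4/+3/−3/+2 points against stated 3+3. With 0.33 for 3+3 in Scenario 4, the −3 becomes +1.

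**Benefit of 12 over 9 patients, Scenarios 1 to 4 (points).** Table 13: +5.6/+10.7/+8.2/+5.6, sum 30.1. Cap at the stop, at most 12 per dose: +4.7/+4.2/+2.3/−0.1, sum 11.1. Selection only: +8.6/+8.8/+7.0/+5.3, sum 29.7.

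**The case against.** The strongest reply is that nothing was concealed. Appendix 7 states that the cap applies in the study and was not simulated. That stands: the fault is the missing size and the unqualified conclusions, not concealment.

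The documents also do not say how the cap enters the algorithm. Sections 3.4 and 9.2 read together suggest that an over-cap dose cannot trigger the stop. But Section 9.2 and Appendix 7 word the cap itself as a bar on selection. So no single corrected figure can be claimed. A reader might infer that the Scenario 5 gain is 11 to 18 points with no-MTD 0.41 to 0.50. That range belongs to one reading, and its top end needs more than 12 patients on a dose, against Section 9.3. A reader might likewise infer that the benefit of 12 over 9 patients shrinks in any case. It does not shrink overall if the cap acts only at selection.

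Scenario 5 is a boundary case, with a true rate of 0.32 beside a cap of 0.325. Much of the effect turns on whether exactly one third passes, and Appendix 7's mention of 33.3% leaves that open. Finally, the 35-point gain and the 4 extra patients on average do match Table 12 as reports of the uncapped simulation. They are not misquoted; they describe a different design. The 1.04 row sum is as read from the converted text and could be a one-digit reading error.

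**Conclusion.** The concern holds in this form: Tables 12 and 13 do not describe the design in force, and Appendix 7 does not say by how much. In Scenario 5 at a stop of 9, every reading tried with a 0.325 cap gives a gain of 5 to about 30 points instead of 35, and no-MTD of 0.30 to 0.57 instead of 0.17. Allowing exactly one third does not recover the stated values either. These figures rest on cohorts of 3 in the main runs, the assumed selection estimator, and assumed handling when a dose reaches its patient limit over the cap.

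It would be wrong to infer that mTPI was the wrong choice. It leads the stated 3+3 in all five scenarios when the cap governs the stop and enrolment may continue to 12. The lead becomes doubtful in some scenarios only if the cap acts at selection alone, or forces a step down as soon as the stopping size is reached. Stated overestimation would improve.

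The 13% and 5-patient figures contradict Table 12 on any reading. The Scenario 4 row needs checking against the source output.

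**What to change.** Correct now: the minimum gain to 11 points, the Scenario 5 size difference to about 4 patients, and the Scenario 4 3+3 row after checking the source output.

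Then reconcile three things:
- The cap: 32.5% in Sections 3.4 and 9.2, against 33% and 33.3% in Appendix 7.
- The stopping text in Sections 3.2.2, 3.4 and 9.2.
- The decision tables. As read, protocol Table 2 and Appendix 7 differ at 2/10 and 5/9, and SAP Table 2 differs from protocol Table 2 at 4/7 and 4/10.

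State how the cap enters stopping and selection, which estimator selects the MTD, and what is assumed when a dose reaches 12 patients over the cap. Re-run the existing simulation under those rules and replace Tables 12 and 13. Update the statements on the 35-point gain, the average extra patients and the value of 12 patients from the re-run.

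The cost is the reconciling text in both documents and a re-run of existing code, with no extra patients. Stated accuracy and no-MTD rates will look less favourable, and stated overestimation more favourable.

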## 1. VERSION HISTORY

This is the second version of the statistical analysis plan, based on the protocol dated Jan 12, 2018.

Texts taken directly from the protocol are made *Italicized*.

## 2. INTRODUCTION

This SAP provides the detailed methodology for summary and statistical analyses of the data collected in study B7831001. This document may modify the plans outlined in the protocol; however, any major modifications of the primary endpoint definition or its analysis will also be reflected in a protocol amendment.

### 2.1. Study Objectives

[figure not shown]
#### Part 1 (Dose-Escalation) Primary Objective

- *To assess safety and tolerability of increasing dose levels of PF-06671008 administered in patients with advanced solid tumors for whom no standard therapy is available in order to estimate the Maximum Tolerated Dose (MTD) and select the Recommended Phase 2 Dose (RP2D).*

#### Part 1 (Dose-Escalation) Secondary Objectives

- *To evaluate the overall safety profile;*
- *To characterize the single and multiple dose pharmacokinetics (PK) of PF-06671008;*
- *To evaluate the immunogenicity of PF-06671008;*
- *To document any anti-tumor activity.*

CCI

CCI

**Part 2 (Dose-Expansion) Primary Objective**

- *To confirm safety and tolerability and explore preliminary evidence of anti-tumor activity of PF-06671008 at the RP2D in patients with P-cadherin expressing advanced CRC, TNBC or NSCLC.*

**Part 2 (Dose-Expansion) Secondary Objectives**

[figure not shown]
- *To evaluate the overall safety profile at the RP2D;*
- *To characterize the single and multiple dose PK of PF-06671008;*
- *To evaluate the immunogenicity of PF-06671008;*
- *To evaluate preliminary anti-tumor activity through time to event endpoints.*

CCI

## 2.2. Study Design

This is a Phase 1, open-label, multi-center, multiple-dose, safety, PK [CC1] study of single-agent PF-06671008. This study contains two parts, dose escalation (Part 1) followed by dose expansion (Part 2). Sequential cohorts of patients with tumor types with the potential to have P-cadherin expression, that is resistant to standard therapy or for whom no standard therapy is available will receive escalating doses of PF-06671008, in Part 1 of the study. Part 2 will evaluate the dose selected from Part 1 in patients with P-cadherin expressing TNBC, CRC or NSCLC. The overall study design is depicted in Figure 1 below.

### Figure 1. Overall Study Design

Up to approximately 152 patients are expected to be enrolled in the study overall. The actual number of patients enrolled will depend on the tolerability of PF-06671008 and the number of dose levels required to identify the MTD.

[Reference Source: Protocol Section 3.1]

### 2.2.1. Dose Escalation Phase (Part 1)

*Increasing dose levels of PF-06671008 administered weekly will be evaluated using a modified toxicity probability interval (mTPI) method that targets a MTD associated with a 27.5% probability of DLT. Part 1 will follow a mTPI method initially with cohorts of 1-2 patients each and a primary DLT observation period of 21 days following the first dose (C1D1).*

If a DLT or other toxicities occur (ie, those that have the potential to be DLTs if more severe) during Cycle 1 but prior to the observation of CTCAE Grade  $\geq 2$  cytokine release syndrome (as described below in [Evaluation of a Priming Dose](#)), dose escalation will continue to

follow a mTPI design but with cohorts of 2-4 patients each. The primary DLT observation period will continue to be 21 days following the first dose (CIDI).

Additional patients may be entered at any dose level in the IV and/or SC routes of administration at or below the MTD, after discussion with and permission by the sponsor, to obtain additional safety, PKCCI and anti-tumor activity data. CCI [REDACTED]

[REDACTED] These additional patients will require paired biopsies. Because these additional patients will receive a dose lower than the concurrent dose escalation cohort or will be enrolled at dose following the DLT evaluation period in the first 2-4 patients enrolled, their potential DLT observations may not be strictly used in the mTPI algorithm for the ongoing dose finding. However, the safety profile from these additional patients will be used to establish the MTD or recommended Phase 2 dose (RP2D).

### 2.2.2. Evaluation of a Priming Dose

Based on toxicity study results, the evaluation of a priming dose to allow subsequent higher level dose administration may be instituted in this study. In addition, blinatumomab, an approved bispecific agent for the treatment of ALL, has been able to overcome symptoms of cytokine release syndrome (CRS) with the implementation of a priming dose (Topp et al, 2014). Therefore, this study may implement the evaluation of a priming dose during the escalation phase.

The initial priming dose will be defined to facilitate subsequent dose escalation towards establishing the MTD of a dosing regimen that includes a priming dose. The study aims to determine a MTD for an IV dose regimen that does not include a priming dose, and an independent MTD for an IV dose regimen that includes a priming dose. In addition, the study aims to similarly determine a MTD for PF-06671008 administered subcutaneously that may or may not include a priming dose.

The decision to evaluate a regimen that includes a priming dose may be made by the investigators and sponsor prior to reaching a MTD using the following criteria as guidance:

If a dose level induces symptoms consistent with Grade 3 CRS as defined in the protocol lasting for >24 hours considered not to be due to an infusion related reaction (IRR), allergic reaction, anaphylaxis or other causes in a cohort of 2-4 patients after the initial infusion, an additional 1-4 patients (up to approximately 6 patients overall) will be enrolled at that dose to confirm implementation of a priming dose (Dose Prime) for subsequent cohorts. If an additional confirmed CRS of Grade 3 lasting for >24 hours is observed at that dose, then a lower dose, which has been evaluated in at least 2-4 patients, will be chosen as a priming dose (Dose Prime) for subsequent cohorts. If a Dose Prime is selected, dose escalation will continue to determine the MTD of a dose regimen that includes a priming dose. The evaluation of a Dose Prime may be implemented for both the IV and/or SC routes of administration.

[figure not shown]
*If a dose level induces confirmed CRS of Grade 4 considered not to be due to an IRR, allergic reaction, anaphylaxis or other causes, then a lower dose, which has been evaluated in at least 2-4 patients, will be chosen as a priming dose (Dose Prime) for subsequent cohorts.*

*In addition, observation of a confirmed CRS event that meets the above qualifications following later infusions (ie, after Cycle 1 Day 1) or CRS events that are approaching the limit of tolerability may prompt the investigators and sponsor to include evaluation of a Dose Prime for subsequent cohorts.*

*After confirmation of the safety of Dose Prime, the treatment schedule will implement the inclusion of the fixed priming dose as the first dose (C1D1) followed by a second dose (C1D8) that will continue to be escalated in subsequent cohorts following an mTPI method in cohorts of 2-4 patients. After the MTD has been established, the priming dose may potentially be further verified in connection to the established MTD/RP2D, including consideration of more than one priming step, if indicated, using information from all patients who were included in the initial priming dose determination as well as those enrolled in subsequent dosing cohorts.*

*The primary DLT observation period for cohorts that include Dose Prime will be 21 days following the first dose (C1D1). The dose escalation should a Dose Prime be instituted is depicted in Figure 2.*

